Equipoise: We are in a state of equipoise as the optimal approach to eradicate inhibitors in hemophilia is not known. While a randomized trial established that 200 IU/kg daily has been adopted as the standard of care for immune tolerance induction (ITI). However, only 70-80% respond, and ITI is time intensive, burdensome, taking up to 9-12 months with some requiring ports and lines, and costly. Further, those not tolerized within the first year of inhibitor onset are often refractory to ITI. Thus, simpler, more effective approaches to eradicate inhibitors is critical to improve outcomes. With the availability of Eloctate, small studies of ITI using 100 IU/kg every other day has reduced time to inhibitor eradication by nearly 50%, but these studies were not randomized. Among the reasons time to ITI eradication is long is the problem of breakthrough bleeds, which may activate the immune system "danger", and thus, use of Emicizumab by promoting hemostasis and avoiding factor VIII, could potentially reduce bleeds during ITI and reduce time to ITI. However, no data exist on whether Emicizumab reduces time to ITI. However, if breakthrough bleeds occur on Emicizumab, the requirement for FVIII to treat these bleeds could negate the potential effect of Emicizumab on ITI could be lost. In small nonrandomized studies, Emicizuab have indicated it is safe in infants but there are no data and no randomized trials to determine who might benefit or the optimal dose and/or combination of these agents to shorten ITI.

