For these reasons, we will study if *Eloctate* ITI plus *Emicizumab* is superior to *Eloctate* ITI alone in eradicating inhibitor formation in patients with severe hemophilia A and inhibitors to FVIII of all ages, and anti-FVIII > 5.0 B.U. when continued weekly for 48 weeks to eradicate inhibitors. We *hypothesize* that *Eloctate* ITI upregulation of T regs, and *Emicizumab* prevention of bleeds ("danger") will be superior to *Eloctate* ITI alone in eradicating inhibitor formation. The concept is innovative, as it combines the "avoidance of danger" concept with the "promotion of tolerizing T regulatory cells" to improve inhibitor eradication. The concept of avoiding FVIII exposure by preventing bleeds with *Emicizumab* during ITI may be important in eradicating inhibitor formation. It's effectiveness in preventing bleeds in hemophilia inhibitor patients makes it a potentially powerful agent in the management of hemophilia, but there are no data on its use in eradicating inhibitors. Further, if it is not successful in preventing breakthrough bleeds during ITI may negate its potential beneficial effect and simpler subcutaneous administration.

Specific Aim 1: To compare *Eloctate* immune tolerance induction (ITI) every-other-day (q.o.d.) plus *Emicizumab* weekly prophylaxis vs. *Eloctate* ITI q.o.d. alone for 48 weeks in eradicating inhibitors in children and adults with severe hemophilia A in the Eradication Trial. We will conduct this multi-center, randomized phase III clinical trials at up to 41 HTC sites, with the same study visit frequency, blood sampling, and lab assays as in the companion Prevention Trial (PRO 19040140). The primary endpoint in the Eradication Trial is the eradication of anti-FVIII antibody < 0.6 BU by chromogenic Nijmegen-modified Bethesda assay (CBA) by 48 weeks.

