Hypothesis 1: We hypothesize that Eloctate ITI q.o.d. plus weekly Emicizumab is superior to Eloctate ITI q.o.d. alone in eradicating inhibitors, anti-FVIII < 0.6 B.U. (CBA), when given for 48 weeks in children and adults with severe hemophilia A and high-responding inhibitors (historic anti-FVIII > 5.0 B.U.). Yet there is equipoise, as while Eloctate ITI may reduce the time to tolerance it is burdensome with qod dosing and data are available from small, nonrandomized studies. While both drugs may shorten ITI and even be synergistic, there is equipoise in the absence of randomized trials. While Emicizumab has been tried in hemophilia A inhibitor patients in small nonrandomized studies, there are no data on whether it reduces time to tolerance. As *Emicizumab* is given subcutaneously weekly, if, when given with *Eloctate ITI*, it was superior to *Eloctate* ITI alone in reducing time to ITI, it would be the "winner" over *Eloctate ITI alone*.

Specific Aim 2: To evaluate the safety and mechanism of inhibitor suppression *eradication* in patients with severe hemophilia A and inhibitors. Secondary endpoints include a) *safety,* measured by number and frequency of bleeding episodes (i.e. hematomas, hemarthroses) and associated factor use and port infections; and b) *mechanism of inhibitor suppression eradication,* measured by FVIII-specific T cell ELISPOT assay; FVIII genotype; HLA type; and chromogenic FVIII trough levels; and by micriobiome stool sample, each compared with anti-FVIII.

Hypothesis 2: We hypothesize that safety, measured by bleeds requiring rescue factor or prophylaxis escalation, and port infections, will not differ between treatment arms; and the mechanism by which *Eloctate* suppresses (prevents, eradicates) inhibitor formation is via Fc induction of regulatory T cells (Tregs) promoting FVIII tolerance, measured by ELISPOT assay. This novel approach to eradicate inhibitors is compelling, and, if successful, will reduce the burden of inhibitor formation and the associated morbidity, hospitalization, cost, and early mortality, and be adopted immediately into clinical practice.

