3.6 Statistical Considerations

The purpose of the **Inhibitor Eradication Trial** is to compare novel agents, *Eloctate ITI* with or without *Emicizumab*, in the eradication of inhibitor formation. The results will be compared with hemophilia genotype, trough FVIII chromogenic activity, HLA, and FVIII-specific T cell response by ELISPOT assay from baseline, in order to determine correlation of each assay with inhibitor development over time by descriptive statistics.

Demographic and other baseline characteristics will be summarized using descriptive statistics or counts and percentages, as appropriate. Data to be tabulated will include, but not be limited to, age, race, height, weight, frequency and site of bleeds (hematoma, joint, CNS), emicizumab use, circumcision bleeding and/or treatment, surgery or procedures. All subjects enrolled in the study and who receive *Eloctate ITI* plus *Emicizumab* or *Eloctate ITI alone* will be included in the evaluation for safety. Data on treatment administration and adherence to assigned treatment will be presented. All subjects enrolled in the study and who receive *Eloctate ITI* with/without *Emicizumab* will be included in the evaluation for safety.

Safety measures will include the number and frequency of bleeding events (hematomas, joint, CNS bleeds) during the 48-week study, and the frequency and time to central line infections. Patient diaries will be reviewed monthly for bleeding frequency and site, and for dose and frequency of treatment. If breakthrough bleeds occur, additional treatment will be given at the discretion of the subject's physician, after which treatment may be continued at least weekly or escalated per physician discretion. Subjects will be closely monitored for adverse events, including allergic reactions, thrombosis, bleeding: these events will be summarized over time on study drug. Adverse events will be evaluated for frequency, relatedness, and severity.

Adverse events will be classified using CTCAE System, Vol 4.03, 2010. Tabulations of adverse events by frequency, relatedness, and severity will be presented. Serious adverse events, laboratory parameters, and vital signs will be presented using descriptive statistics for changes over time. Concomitant medications and physical exam data will be summarized over time.

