Subjects reaching the primary endpoint: The primary endpoint is inhibitor eradication, defined as anti-FVIII < 0.6 B.U., by chromogenic Nijmegen Bethesda assay (CBA). A local lab anti-FVIII < 0.6 B.U. will be repeated on this, or if insufficient, a repeat sample within 7 days, and a second sample obtained within 4 weeks for confirmation. A central lab anti-FVIII < 0.6 B.U. will be repeated within 4 weeks for confirmation. If confirmed, subjects will either continue *Eloctate or rFVIIa* for treatment of bleeds, depending on the inhibitor titer per discretion of the subject' treating physician, but remain on study follow-up through week 48. For clarification, time to peak FVIII >60% will be determined at subsequent testing after confirmation of anti-FVIII < 0.6 B.U. Prognostic factors collected at baseline, including age, race, family history of inhibitors, current or past emicizumab use, and past circumcision, will be compared by treatment arm.

The **Secondary Endpoints** include a) safety measured by the number and frequency of bleeding events (hematoma, joint, CNS bleeds), the frequency and time to central line infections; and the number and frequency of allergic reaction, and thrombosis; and b) mechanism of inhibitor prevention by FVIII-specific T cell ELISPOT (Ig, RNA), performed on an aliquot of PBMCs; and genotype, HLA, and trough chromogenic FVIII drawn on the buffy coat of anti-FVIII plasma samples. ELISPOT assays will be performed on T cell populations depleted of regulatory T cells (T reg) (CD4+CD25+FoxP3+) to determine the role of T regs in controlling immune response to FVIII.

Analysis of Secondary Endpoints: The trial is not powered to analyze secondary endpoints statistically, but will collect these endpoints and perform descriptive statistics and correlations of safety and T cell mechanism by study arm, and with hemophilia genotype, HLA, and antigen-specific (FVIII) T cell responses (ELISPOT) from baseline, in order to determine correlation of each assay with inhibitor development over time by descriptive statistics.

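### Hypothesis 2 predicts no difference in bleeds, against the bleed-prevention rationale for Arm A, and the descriptive secondary analysis can neither support that prediction nor size a reduction

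*Combined protocol and SAP*

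**What the plan says.** **Prediction for bleeds.** Hypothesis 2 in section 2.1 states that safety, "measured by bleeds requiring rescue factor or prophylaxis escalation, and port infections, will not differ between treatment arms".

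**Rationale for Arm A.** The Equipoise paragraph of section 2.1 says that "use of Emicizumab by promoting hemostasis and avoiding factor VIII, could potentially reduce bleeds during ITI and reduce time to ITI". Later in the section: "The concept of avoiding FVIII exposure by preventing bleeds with *Emicizumab* during ITI may be important in eradicating inhibitor formation". The section also allows for failure: "if it is not successful in preventing breakthrough bleeds during ITI may negate its potential beneficial effect". Section 3.4 describes Emicizumab as effective in bleed prevention. Section 4.5 (Potential Benefits) lists fewer bleeds as a possible benefit, though it credits both drugs.

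**Analysis.** Section 3.6 says: "The trial is not powered to analyze secondary endpoints statistically, but will collect these endpoints and perform descriptive statistics and correlations", by study arm. It gives no equivalence margin, model or interval for bleeds.

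**Bleed measure.** Specific Aim 2 uses "number and frequency of bleeding episodes (i.e. hematomas, hemarthroses) and associated factor use and port infections". Section 3.6 (Safety measures) uses "number and frequency of bleeding events (hematomas, joint, CNS bleeds) during the 48-week study". The Protocol Summary and section 1.0 also list hematoma, joint and CNS bleeds. Hypothesis 2 uses only bleeds that lead to rescue factor or stepped-up prophylaxis.

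**The concern.** Eloctate ITI is the same in both arms, so preventing bleeds is the specific contribution that the rationale assigns to Emicizumab. Bleeding by arm is therefore the direct evidence on whether the first step of that rationale occurred. The plan classes it as safety and predicts a null result.

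Two problems follow. A real fall in bleeds in Arm A would agree with the rationale and contradict Hypothesis 2. A wide, inconclusive comparison would leave Hypothesis 2 neither supported nor refuted, because no margin defines what counts as not differing and no interval shows what the data exclude. Either way the report could not say clearly how much bleeding changed.

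**Working it through.** **1. The plan's own figure.** No power or precision is stated for bleeds. The only power figure, at least 80%, belongs to eradication (95% against 80% inhibitor-free, 90 subjects, 1:1, two-sided 5%). A constant-hazard check:

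- hazard ratio = ln(0.05)/ln(0.20) = 1.861
- expected events = 45 × 0.95 + 45 × 0.80 = 78.75
- power = Φ(√(78.75/4) × ln 1.861 − 1.96) = Φ(0.797) = 78.7%

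A simplified simulation of the two-look rule (99.5% interim, 97.9% final; exponential model, uniform six-year accrual, no dropout) gave about 77% power and 4.8% type I error. Hypothesis 1 thus has a formal test with roughly the stated properties. The bleed part of Hypothesis 2 has none.

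**2. Direction.** Section 2.1 expects, with hedging, fewer bleeds in Arm A. Hypothesis 2 in the same section expects equal bleeds. Hypothesis 1 concerns anti-FVIII below 0.6 B.U. and does not mention bleeds. The conflict is between Hypothesis 2 and the rationale, not between the two hypotheses.

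**3. Precision if bleed rates are truly equal.** From the documents: 90 subjects at 1:1, so 45 per arm. Assumed: mean μ of 2, 4 or 8 bleeds per subject over 48 weeks, negative binomial dispersion k of 0.5, 1 or 2, and complete follow-up.

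SE(log rate ratio) = √[(1/μ_B + k + 1/μ_A + k)/45]; 95% interval = exp(±1.96 × SE).

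| μ | k | SE | 95% interval around a ratio of 1 |
|---|---|---|---|
| 8 | 0.5 | √(1.25/45) = 0.167 | 0.72–1.39 (narrowest) |
| 4 | 1 | √(2.5/45) = 0.236 | 0.63–1.59 |
| 2 | 2 | √(5/45) = 0.333 | 0.52–1.92 (widest) |

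Even the narrowest interval leaves open a fall of 28% or a rise of 39%.

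**4. The same question with proportions.** Assume 20% to 70% of subjects have a qualifying bleed. The half-width 1.96 × √[2p(1 − p)/45] is 17 points at p = 0.2 and 21 points at p = 0.5. With two one-sided 5% tests, the power to show equivalence is 0% for a 10-point margin, 0–11% for 15 points and 20–53% for 20 points.

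**5. Follow-up time.** Section 3.2 follows subjects for 48 weeks or until eradication, and starts the post-treatment period at week 48 or at eradication. Its text on subjects reaching the primary endpoint, and section 3.6, keep them in follow-up to week 48. If follow-up ends at eradication in practice, observation time will differ by arm whenever eradication does, and raw bleed counts will not be comparable.

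**The case against.** The strongest reply is that this is a wording conflict in an unpowered secondary hypothesis. The rationale is hedged, section 3.6 says openly that secondary endpoints are descriptive, bleeds will be summarised by arm, and nothing says that a non-significant result will be declared no difference. All of that is true, and the primary endpoint, sample size and stopping thresholds are unaffected. But a hedged expectation of fewer bleeds still conflicts with a prediction of equal bleeds, and a summary by arm without an interval does not let a reader judge either.

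Three stronger readings are tempting, and the documents do not support them.

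- *Hypotheses 1 and 2 cannot both be true.* A reader might infer this, but Hypothesis 1 is about eradication only. Better eradication with similar bleeding is logically possible, and section 2.1 allows that the drugs may be synergistic.
- *The plan can test neither hypothesis.* Eradication has a formal Bayesian test in section 3.6. Only the bleed statement lacks one.
- *The statement that secondary endpoints are not powered is false for bleeds.* This depends wholly on assumed rates. On the grid above, power for a true ratio of 0.5 ranges from 51% to 98% and falls below 80% in four of nine cells. For a ratio of 0.6 it is below 80% in eight of nine, and for 0.7 in all nine. Only an assumed ratio of 0.3 gives at least 90% throughout.

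The definitions also differ less than they first appear. Hemarthroses are joint bleeds, so Aim 2 differs from section 3.6 only by leaving out CNS bleeds. The real outlier is the rescue-or-escalation count in Hypothesis 2.

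**Conclusion.** The point holds in this form. Hypothesis 2's prediction of no difference in bleeds conflicts with the bleed-prevention rationale for Arm A, and a descriptive analysis with no margin or interval can neither support that prediction nor quantify a reduction. With 45 per arm, the 95% interval around equal rates runs from 0.72–1.39 to 0.52–1.92 over the assumed means and dispersions; dropout would widen it. The documents give no bleed rate, dispersion or margin, so these figures are illustrative, but equality could not be shown with any precision anywhere in the range.

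The eradication test stands. The change is worth making because bleeding is the first step of the trial's own rationale and the data will be collected anyway. A bleed rate ratio would show whether bleeding fell. It would not show that fewer bleeds caused eradication.

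**What to change.** 1. **Section 2.1, Hypothesis 2.** Remove bleeds and port infections from the no-difference statement. State that bleeds will be estimated by arm, with fewer expected in Arm A under the section's own rationale.
2. **Section 3.6, Analysis of Secondary Endpoints.** Report the Arm A to Arm B bleed rate ratio with a 95% interval from negative binomial regression, with log follow-up time as offset and adjustment for the past-bleed history taken at screening. Label it as estimation, not a powered test. Reconcile the passages on whether follow-up ends at eradication or at week 48.
3. **One bleed definition** in the Protocol Summary and sections 1.0, 2.1 and 3.6. For example, keep the protocol's hematoma, joint and CNS bleeds as the main count, with bleeds needing rescue factor or escalation as a second count. Note that the second count depends on physician discretion in an open-label trial.
4. **Port infections.** Report an estimate by arm with an interval.

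The cost is wording changes and one extra secondary model. The diaries already record bleeds and treatment, and past bleeds are taken at baseline, so no new data, visits or patients are needed.

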3.0 Research Design and Methods

3.1 Drug/Device Information

Eloctate (rFVIIIFc) and *Emicizumab* (hemlibra) are FDA-approved for the prevention and/or treatment of bleeds in hemophilia A, and are safe and effective in adults, adolescents, and children. For this trial, subjects will use their own supply of study drug to which they are randomized. Clinical trials of *Eloctate* and *Emicizumab* in adults and children with severe hemophilia A have demonstrated safety and efficacy when used to prevent bleeds or promote hemostasis. In this trial, subjects will use *Eloctate* ITI (immune tolerance induction) with or without *Emicizumab* to eradicate inhibitors: this approach is supported by preliminary data from anecdotal small, non-randomized studies. Subjects will maintain a home inventory of the study drug(s) to which they are randomized. *Eloctate* in vial sizes of approximately 250, 500, and 750 is available for children, and 1000, 1500, 2000, 3000 IU for adults: a two-way needle will allow transfer of the diluent into the lyophilized powder for reconstitution and slow infusion over 5-10 minutes. *Emicizumab* in vial sizes of approximately 30 mg per ml, 60 mg per 0.4 ml, 105 mg per 0.7 ml, and 150 mg per ml is available for children and adults: a tuberculin syringe will allow transfer of the drug from the vial for subcutaneous injection over 1-2 minutes. Study drug(s) will be available by physician prescription which can be filled at the HTC pharmacy or at another pharmacy of the patient's or parent/caretaker's choice.

Once a subject is consented and identified as eligible for the trial, a unique subject number will be assigned to each subject by the Data Coordinating Center (DCC), Graduate School of Public Health (GSPH), University of Pittsburgh, Pittsburgh, PA. Study drug dosing will be given by the hemophilia center nurse, clinic or hospital infusion center, or, if on home treatment, by patient or parent/ care provider, or visiting nurse, in the usual manner: this is either by intravenous infusion (*Eloctate*) over 5-10 minutes through a winged infusion needle (butterfly) heplock placed in the forearm, or, if required, a central line; or by subcutaneous injection (*Emiczumab*) over 1-2 minutes with a tuberculin syringe in the abdomen or thigh. This study site will maintain accurate records, demonstrating dates, times, and doses administered, and patients or parent/caretakers will maintain a diary to record this information.

3.2 Research Design and Methods

This is a 48-week outpatient, randomized phase III clinical trial that employs Bayesian Platform design to assess inhibitor eradication in patients with severe hemophilia A, FVIII <0.01 IU/ml, and a current or past high-responding inhibitor (anti-FVIII >5.0 B.U.), ITI-refractory or ITI-naive. Because hemophilia is a rare disease, we incorporated Bayesian Platform design and will use historical and prospective ongoing clinical trial data on inhibitor formation (Bayesian "priors") to efficiently use rare patients and increase power. The Inhibitor Eradication Trial is linked to the Inhibitor Prevention Trial, and the trials are integrated so there is efficiency and economy, using the same HTCs, staff, frequency of blood sampling, visits, data collection, and lab assays. The Eradication Trial is a randomized phase III open-label trial designed to evaluate the efficacy of *Eloctate* immune tolerance induction (ITI) (100 IU/kg every other day) plus weekly *Emicizumab* 1.5 mg/kg weekly (after a 4-week induction) vs. Eloctate ITI alone (100 IU/kg every other day), to eradicate inhibitor formation in adults or children with severe hemophilia A and current or past high-responding inhibitors to FVIII, anti-FVIII \geq 5.0 B.U. Approximately 2-4 children or adults with severe hemophilia A and inhibitors will be recruited at each HTC. The study drugs will be administered to each subject for up to 48 weeks. *Eloctate* will be given either by weekly intravenous infusion over 5-10 minutes, and (Eloctate) will be given by weekly subcutaneous injection over 1-2 minutes. For treatment of breakthrough bleeds, for safety reasons, rFVIIa will be given by intravenous infusion over 5-10 minutes at 90 mcg/kg per standard of care, at MD discretion, or if the inhibitor titer has fallen, additional Eloctate will be given, per MD discretion. The treating physician may be the study physician. FEIBA will not be allowed on the trial as it may result in thrombosis or thrombotic microangiopathy in patients taking Emicizumab. All bleeds and study drug(s) will be recorded by patient or parent/ caretaker for each subject in a patient diary. All randomized subjects will be followed 48 weeks or until they reach the study outcome of inhibitor eradication. Follow-up visits will be monthly until end-of-study, week 48.

The Data Safety Monitoring Board (DSMB) will be responsible for reviewing all data generated for the study interventions, from the time of dosing through the end of each 48-week trial. Each study will consist of three phases; a Screening Period, a Treatment Period, and a Post-Treatment Period.

Screening Period: Subject eligibility for the study will be determined prior to study drug dosing. A history of past bleeds, factor treatment, and circumcision bleeding and treatment will be obtained. A baseline blood sample will be collected for anti-FVIII inhibitor titer by chromogenic Nijmegen Bethesda (CBA) assay, FVIII-specific T cell (ELISPOT), trough

FVIII (chromogenic assay), HLA, hemophilia genotype, and sample storage for future testing. A microbiome stool sample will also be obtained. A baseline height, weight and brief physical exam will be obtained.

Treatment Period: After random assignment to one of the two treatment regimens, the treatment period will extend for up to 48 weeks, beginning with every other day *Eloctate* ITI plus weekly *Emicizumab or* with *Eloctate* ITI alone. If a breakthrough bleed occurs during the trial, in the presence of an inhibitor, rFVIIa may be used as needed up to 4 times daily until resolution, per physician discretion. *FEIBA will not be allowed on the trial as it may result in thrombosis or thrombotic microangiopathy in patients taking Emcizumab*. If a breakthrough bleed occurs in the absence of an inhibitor (e.g. if it has resolved), either *Eloctate* (65 IU/kg) or rFVIIa (90 µg/kg) may be used to treat bleeds, per physician discretion.

The frequency and number of inhibitors that are tolerized (eradicated) will be analyzed in subjects by assigned treatment during the study; if a subject receives another clotting protein for any reason, he will be monitored and followed to 48 weeks and included in the primary intention-to-treat analysis. All bleeds and factor/drug use will be recorded in a patient diary. Height, weight, and a brief physical exam will be performed every month at routine study visits, and factor supply reviewed for each study subject, and, if necessary, reordered at that visit. Laboratory assays including anti-FVIII inhibitor by chromogenic Nijmegen modified Bethesda (CBA) assay, antigen-specific T cell assays (ELISPOT), hemophilia genotype, trough FVIII (chromogenic assay), and sample storage for future studies will be obtained at baseline and at week 4, 12, 24, 36, and 48. Hemophilia genotype and HLA will be performed at baseline only. All samples must be drawn before the study drug dose.

Post-Treatment Period: The post-treatment period begins after the last day of study follow-up at week 48 or when the inhibitor is eradicated. All clinical and lab data will be reviewed and entered on the INHIBIT Trial DCC Data Management System website through the end of the entire study period.

This is a randomized Phase III Clinical Trials Platform that includes 2 clinical trials, the **Prevention Trial** (PRO19040140) and the **Eradication Trial** (PRO19070800) in a rare population which utilizes the same HTCs, sampling time, volume, and frequency, visits, and lab assays to enhance trials efficiency. In the **Eradication Trial**, study drug will be initiated as early as the day of enrollment and randomization. Subjects will receive *Eloctate* ITI 100 IU/kg every other day plus weekly *Emicizumab* 1.5 mg/kg (after standard 3.0 mg/kg/wk x4 wk induction) or *Eloctate* ITI 100 IU/kg every other day alone. The doses of these drugs are consistent with standard of care guidelines for bleed eradication (immune tolerance). Subjects will receive the drug(s) to which they are randomized, preferably between 7 am and 9 am on days they are given and continued through study week 48. All bleeds and factor use will be recorded in the Subject Diary. This is an open-label trial, so subjects enrolled on the study will receive study drug by physician prescription. Baseline variables, all potential risk factors, including age, family history of inhibitors, race, and circumcision, will be collected prior to randomization and prior to initiating study drug. (Circumcision is commonly performed in over 50% of children with hemophilia in the U.S., but not an established risk for inhibitor formation).

Bleeding Episodes Occurring during Study

For breakthrough bleeds occurring during the study, *Eloctate* 65 IU/kg will be the treatment of choice for non-inhibitor or tolerized inhibitor patients (BU< 0.6 BU), while rFVIIa 90 mcg/kg will be the treatment of choice for inhibitor patients unresponsive to *Eloctate* or FVIII, per discretion of the treating physician (may be the study physician). The HTC coordinator will review study drug(s) supply with the patient/ parent/ caretaker to assure they are re-ordered when three doses are left. There will be no change in study visits.

Subjects Developing the Primary Endpoint

The primary endpoint will be eradication of an inhibitor, defined as anti-FVIII < 0.6 B.U. by chromogenic Nijmegen Bethesda assay (CBA). A local lab anti-FVIII < 0.6 B.U. will be repeated on this sample or, if insufficient, a repeat sample within 7 days, and a second sample obtained within 4 weeks for confirmation. A central lab anti-FVIII < 0.6 B.U. will be repeated within 4 weeks for confirmation. A central lab anti-FVIII < 0.6 B.U. will be repeated within 4 weeks for confirmation. A central lab anti-FVIII < 0.6 B.U. will be repeated within 4 weeks for confirmation. All subjects whose inhibitor is eradicated will remain on study follow-up to week 48. Additional tests will be done, per standard of care, including peak and trough to advise when ITI can be stopped and regular prophylaxis can begin. Subjects whose inhibitor is eradicated, i.e. anti-FVIII < 0.6 B will receive *Eloctate* with/without *Emicizumab*, per physician discretion, to treat or prevent bleeds: if bleeding occurs that is unresponsive to *Eloctate* with/without *Emicizumab*, rFVIIa will be used. FEIBA will not be allowed on this trial for safety reasons.

It is anticipated that 2-4 subjects will be enrolled locally, contributing to the overall study enrollment of 90 subjects at one of up to 41+ participating HTCs. The duration of the study is approximately 48 weeks per subject, with an expectation the study will last up to 7 or more years, subject to enrollment and completion of all procedures. For this study, all study visits will occur at the HTC.

SCREENING VISIT, RANDOMIZATION, AND INITIATION OF ASSIGNED TREATMENT Study Visit 1, Screening/ Baseline Visit, Wk 0

This visit will take place prior to administration of *Eloctate* with/without *Emicizumab* in order to confirm eligibility requirements. Randomization and initiation of treatment may occur at this visit or within 4 weeks of the visit. The following tests or assessment will be performed at the Screening/ Baseline Visit.

- Study physicians will discuss the study with the patient or parent/caretaker of potential study subjects, answer questions and assure there is adequate time for the patient or parent/caretaker to decide about participation in the study. The patient or parent/caretaker may sign the consent or take the consent with them to discuss with family members and/or other members of their healthcare team. If the patient or the parent/ caretaker is interested in study participation, they may sign the consent and they or the child considered enrolled in the trial. No study procedures will occur until after the patient or parent/care giver has signed the consent document.
- Subjects currently receiving *Emicizumab* will be asked to discontinue the medication prior to randomization. If the subject or parent/caretaker is not willing to discontinue treatment, they will be deemed ineligible. If a subject discontinues *Emicizumab* prior to randomization, there is no need for a washout period and there are no known risks of stopping *Emicizumab*. It is possible that bleed frequency could increase if prophylaxis (eg. factor VIIa) is not given or infrequently given due to the more difficult intravenous route factor VIIa than *Emicizumab*. If a bleed occurs, factor VIIa will be given per physician discretion until it resolves and monitored by home treatment records, per standard of care.
- Demographics of the subject will include age, date of birth, race, and hemophilia genotype, if known.
- Other medical and surgical history of the subject will include height, weight, past bleeds, circumcision, and past factor treatment, dose and frequency.
- Hemophilia diagnosis by history, with historical laboratory test result for confirmation.
- Medication history including all concomitant medications within 4 weeks of the first dose of study drug.
- Brief physical exam including vital signs, height (cm) and weight (kg).
- Blood draw: A 3.8 ml (¾ tsp) blood sample will be collected for anti-FVIII chromogenic Nijmegen Bethesda (CBA) assay (plasma), antigen-specific (FVIII) T cell ELISPOT assay (PBMC), HLA and hemophilia genotype (buffy coat of the plasma sample), trough FVIII chromogenic activity (aliquot of plasma), and a sample (plasma) stored for future studies. All samples must be drawn prior to the study drug dose. Amounts of blood drawn will be less for children weighing less than 14 pounds. The Appendix detailing timing of visits and blood draws is attached at the end of this protocol.
- The samples (all de-identified) and labeled with subject ID number will be processed, frozen, and shipped to a repository in the Coagulation Laboratory at Vitalant, Pittsburgh PA, under the direction of [name]. The inhibitor titer will be run by chromogenic Nijmegen Bethesda (CBA) assay real time, with confirmation on stored aliquots for those testing negative (< 0.6 B.U.). An aliquot of plasma sample will be assessed for trough FVIII chromogenic assay (aliquot of plasma sample). The micriobiome (stool) sample will be shipped to the Vitalant Lab and transported to the microbiome, Vascular Medicine Institute (VMI), Pittsburgh, under the direction of [name]. The PBMC sample will be snap frozen in dimethyl sulfoxide (DMSO) and stored in liquid nitrogen until batch testing for antigen-specific (FVIII) T cell responses by ELISPOT assay in the research laboratory of [name], Uniformed Services of the Health Sciences (USUHS), Bethesda, MD. Samples for future testing (for hemophilia genotype or immunologic studies) will be stored indefinitely.

- Stool sample: A small stool sample will be collected at home to assess genes and bacteria in the gut (micriobiome) and placed in a small tube and returned in a container mailer to Vitalant, and couriered to VMI, Pittsburgh PA.
- After the study physician determines eligibility, the subject will be **randomly assigned to one of the two treatment strategies**, *Eloctate ITI* plus *Emicizumab* or *Eloctate ITI alone*.
- The patient or parent/caretaker will obtain *Eloctate* with/without *Emicizumab* by physician prescription through a clotting factor pharmacy of their choice. *Eloctate* will be administered by venipuncture, using a winged infusion needle (butterfly needle), heplock, or, if required, by central line per physician discretion, over 5-10 minutes. *Emicizumab* will be administered by subcutaneous injection, using a small tuberculin needle over 1-2 minutes. It is anticipated in children and some adults that all study drug doses will be administered in the Hemophilia Center, or, for those living a distance away from the HTC, at a nearby infusion center, emergency room, by patient or parent/ caretaker if trained, or by a visiting nurse.
- All doses of study drug(s), including day, date, time, and dose will be recorded in subject diaries. All bleeds, including day, date, site, and resolution will be recorded by the patient or parent/caretaker. All diaries will be returned to the HTC nurse coordinator at the monthly visits.
- Subjects will begin *Eloctate* with/without *Emicizumab*, with the first dose as early as the day of consent and randomization, should the subject already have received a prescription and supply of study drug as part of standard care; otherwise, study drug(s) may be started as soon as the prescription is received.
- The weekly dose of study drug, 100 IU/kg *Eloctate ITI* with/without 1.5 mg/kg *Emicizumab* (following the 3.0 mg/kg weekly x 4 weeks induction), will be begun following enrollment and screening. The HTC nurse will discuss study visit scheduling with the patient or parent /caretaker. The Screening/ Baseline visit, which may include randomization ant treatment initiation, will last approximately 1 hour.

FOLLOW-UP VISITS:

Study Visit 2: Week 4 (Month 1) Follow-up Visit

- Subject diaries will be reviewed for accuracy and completeness. Data will be extracted for frequency, type, and site of bleeds, including site, and for factor usage by day, date, time, and dose.
- Study drug(s) use will be reviewed and more *Eloctate* with/without *Emicizumab* ordered as needed.
- Concomitant medications will be recorded.
- Assessment for adverse events will be completed.
- Vital signs [blood pressure (BP), pulse (P), respiratory rate (RR), and oral temperature (°C)] will be taken, and weight (kg) will be obtained.
- A 3.8 ml (³/₄ tsp) blood sample will be collected for anti-FVIII chromogenic Nijmegen Bethesda assay (plasma), antigen-specific (FVIII) T cell ELISPOT assay (PBMC), trough FVIII chromogenic activity (aliquot of plasma), and a sample (aliquot of plasma) stored for future studies (for hemophilia genetic or immunologic studies). All samples must be drawn prior to the *Eloctate* with/without *Emicizumab* dose.

Study Visits 3, 5, 6, 8, 9, 11, 12: Monthly Follow-up Visits (Can be done remotely or in person)

- Subject diaries will be reviewed for accuracy and completeness. Data will be extracted for frequency and type of bleeds including site, and for factor usage by day, date, time, and dose.
- Study drug(s) use will be reviewed and more *Eloctate* with/without *Emicizumab* ordered as needed.
- Concomitant medications will be recorded.
- Assessment for adverse events will be completed.

Study Visits 4, 7, 10: Quarterly Follow-up Visits

- Subject diaries will be reviewed for accuracy and completeness. Data will be extracted for frequency, type, and site of bleeds, including site, and for factor usage by day, date, time, and dose.
- Study drug(s) use will be reviewed and more *Eloctate* with/without *Emicizumab* ordered as needed.
- Concomitant medications will be recorded.
- Assessment for adverse events will be completed.
- Vital signs [blood pressure (BP), pulse (P), respiratory rate (RR), and oral temperature (°C)] will be taken, and weight (kg) will be obtained.

A 3.8 ml (¾ tsp) blood sample will be collected for anti-FVIII chromogenic Nijmegen Bethesda assay (plasma), antigen-specific (FVIII) T cell ELISPOT assay (PBMC), trough FVIII chromogenic activity (aliquot of plasma), and a sample (aliquot of plasma) stored for future studies (for hemophilia genetic or immunologic studies). All samples must be drawn prior to the *Eloctate* with/without *Emicizumab* dose.

END-OF-STUDY VISIT

Study Visit 13: Week 48, End-of-Study Visit

- Subject diaries will be reviewed for accuracy and completeness. Data will be extracted for frequency, type, and site of bleeds, including site, and for study drug(s) usage by day, date, time, and dose.
- Study drug(s) use will be reviewed.
- Concomitant medications will be recorded.
- Assessment for adverse events will be completed.
- Vital signs [blood pressure (BP), pulse (P), respiratory rate (RR), and oral temperature (°C)] will be taken, and weight (kg) will be obtained.
